#### 7.12 Drug abuse, misuse, overdose and medical errors

Events related to drug abuse, misuse, overdose and medical errors should be reported to the sponsor.

AEs and SAEs related to drug abuse, misuse, overdose and medical errors should be recorded and reported according to corresponding requirements.

Note: Unintentional missing drug does not belong to medical error that must be reported.

# 8 Subject Withdrawal and Replacement

# 8.1 Subject withdrawal

Subjects can withdraw from the study or discontinue study treatment at any time. As long as clinical condition of subjects support, the investigator can discontinue subjects' treatment at any time. Reasons for subjects' treatment discontinuation or withdrawal from study may include the following types:

• Adverse Event

- Death
- Lost to Follow-up
- Poor compliance
- Investigator's decision
- Pregnancy
- After the first progressive disease based on independent radiology review, subjects who are unsuitable for dose escalation or continuing treatment at the original dose as per the investigator's assessment should discontinue the treatment.
- Progressive disease occurs again based on the investigator's assessment after increasing the dose to 150 mg BID.
- Protocol deviation
- Site Closure by Sponsor
- Termination of the study by the sponsor
- Subject's requests to withdraw
- The investigator considers the subject must discontinue the treatment for the subject's benefit.

If the subject discontinues treatment for reasons other than progressive disease, death, withdrawal of informed consent and lost to follow-up, the subject should receive radiographic examination for tumor assessment by independent radiologic review (IRR) after treatment withdrawal according to the frequency consistent with that during the study until presence of disease progression meeting "RECIST v1.1-GIST Specific Standard" or until starting of new anti-tumor therapy, whichever is the first.

If the subject voluntarily withdraws from the study, the investigator should contact the subject and ask the subject the reasons for treatment discontinuation and request the subject to return to study site to finish end of treatment visit (EOT) and safety follow-up and afterwards receive survival follow-up.

Subjects who discontinue treatment for other reasons must receive end of treatment (EOT) visit and safety follow-up and afterwards receive survival follow-up.

Patients should be asked to return all unused investigational drugs as far as possible.

In any case, the patient's final condition, particularly safety information, should be fully documented as far as possible.

# 8.2 Subject replacement

The study does not allow subject substitution.

# 9 Statistical Analysis

Please refer to Statistical Analysis Plan (SAP) for details of statistical analysis. Statistical Analysis Plan will be finalized before database locking. All changes in previously defined analytical procedures will be described in the final clinical study report (CSR).

Data cutoff of the study is 6 cycles after the last subject has been enrolled to the study or the time when at least 21 cases of IRR-based PFS have occurred in all enrolled patients, whichever occurs first, and the data will be locked for analysis.

# 9.1 Determination of sample size

This phase 2 bridging study is to prove the efficacy of DCC-2618 in Chinese patients is consistent with or similar to that in global patients using the primary endpoint of progression-free survival (PFS) on the basis of independent radiologic review.

Standard definition of bridging study success (consistent or similar): mPFS of ripretinib in Chinese patients will be statistically longer than 1 month, that is, the lower limit of bilateral 90% confidence interval of the observed mPFS is longer than 1 month. Statistical hypothesis: H0: mPFS is 1 month; Ha: mPFS is 2.5 months; bilateral significant level is 0.1; assumed enrollment duration is 6 months; follow-up duration is 2 months; drop-out rate is 15% under at least a 90% test power; approximately 35 subjects should be enrolled to meet the test purposes.

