# **Protocol Synopsis**

· · · · · · · · · · · · · · · · · · ·	ГП
	In this study, progression free survival (PFS) based on independent radiologic review is the primary efficacy indicator and RECIST v1.1-GIST Specific Standard is used for tumor efficacy assessment.
	After being fully informed, signing the informed consent forms and passing the screening, the subjects will receive DCC-2618 (150 mg, QD) continuously until the occurrence of an event for treatment termination as specified in the protocol, 28 days as a treatment cycle, followed by a safety follow-up period until 30 days after the termination of study treatment.
	During the study period, the subjects will be subject to visits as scheduled in the protocol. On the day of the scheduled visit as per the protocol, the subjects should bring the drug to the study site, where they will complete all the pre-dose examinations, and take the drug of the day after being suitable to continue the administration, in the discretion of the investigator. In the first four cycles (inclusive), an radiographic examination will be performed within $\pm 7$ days of each cycle and tumor efficacy will be assessed according to RECIST v1.1-GIST Specific Standard. After that, it should be performed within $\pm 7$ days every two cycles.
	If the subject discontinues treatment for reasons other than progressive disease, death, withdrawal of informed consent and lost to follow-up, the subject should receive radiographic examination for tumor assessment by independent radiologic review (IRR) after treatment withdrawal according to the frequency consistent with that during the study until presence of disease progression meeting "RECIST v1.1-GIST Specific Standard" or until starting of new anti-tumor therapy, whichever is the first.
	Based on independent radiologic review, if a subject has a radiologically confirmed progression disease (PD), the subject can choose:
	• To continue DCC-2618, at an increased dose of 150 mg BID, until the occurrence of an event for treatment termination as specified in the protocol; in the case of the efficacy evaluation for such patient, the lesion diameter before the increase of dosage (but not screening period) should be taken as the baseline value.

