17. Radiographic examination during the Screening Period should cover the chest, the abdomen and the pelvis (within 21 days before the first dose). Only abdomen and pelvis are examined during the study; for patients with pulmonary metastases in the screening period or pulmonary metastases symptoms during the study at the investigator's discretion, chest examination should be performed during the study. It is performed once in each of the first four cycles (including Cycle 4), and then once in every two cycles (e.g., Cycles 6, 8 and 10). Initial evaluation of CR or PR should be conformed 4 weeks later at least. Enhanced scanning is required for the examination. MRI may be applied to subjects allergic to CT enhancer to examine the abdomen and the pelvis, with plain CT scanning for the chest. Ensure consistency in examination means during the study. No ultrasonic examination is allowed. If the subject discontinues treatment for reasons other than progressive disease, death, withdrawal of informed consent and lost to follow-up, the subject should receive radiographic examination for tumor assessment by IRR after treatment withdrawal according to the frequency consistent with that during the study until presence of disease progression meeting "RECIST v1.1-GIST Specific Standard" or until starting of new anti-tumor therapy, whichever is the first.

Abbreviations	Chinese Terminology
AE	Adverse Event
ALT	Alanine aminotransferase
AML	Acute myeloid leukemia
ANC	Neutrophil count
APTT	Activated partial thromboplastin time
ASM	Aggressive systemic mastocytosis
AST	Aspartate aminotransferase
ATC	Chemical drug classification system
AUC	Area under the concentration-time curve
β-hCG	Human Chorionic Gonadotropin
BCRP	Breast cancer resistance protein
BID	Twice daily
BP	BP
CI	Confidence interval
CL/F	Apparent plasma clearance
C max	Maximum concentration
СРК	Creatine kinase
CR	Complete response
CSF1R	Macrophage colony stimulating factor receptor
СТ	Computed tomography
CTCAE	Common Terminology Criteria for Adverse Events
СҮР	Cytochrome P450
DCR	Disease control rate
DLT	Dose-limiting toxicity
ECG	Electrocardiogram
ECOG	Eastern Cooperative Oncology Group
eCRF	Electronic Case Report Form
EMA	European Medicines Agency
ЕОТ	End of Study Treatment
ESMO	European Society for Medical Oncology
FDA	Food and Drug Administration

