## 1.3.1.3.2 Study DCC-2618-03-001

Only efficacy data (n = 129) in the double-blind stage as of 31 May 2019 are listed. The median (95% CI) of PFS in the ripretinib group was 27.6 (20.0, 29.9) weeks and that in the placebo group was 4.1 (4.0, 7.3) weeks. Risk of disease progression or death in patients who received ripretinib treatment decreased by 85%, showing statistically significant difference with the placebo group (HR 0.15; stratified log-rank test P < 0.0001). At week 26, 51.0% of patients receiving ripretinib treatment and 3.2% of patients receiving placebo didn't have disease progression (estimated PFS rate).

Confirmed ORR was 9.4% in the ripretinib group and 0% in the placebo group (P = 0.0504, Fisher's exact test); however, statistical significance was not reached.

OS results of the placebo group included OS data of patients in the placebo group who

received ripretinib treatment crossly after IRR-assessed disease progression. During the final analysis, 29 patients (65.9%) in the placebo group were subject to crossover treatment in the treatment group and received at least one dose of ripretinib. Of 85 patients in the ripretinib group, 26 patients (30.6%) experienced OS events and 59 patients (69.4%) were censored. Of 44 patients in the placebo group, 26 patients (59.1%) experienced OS events and 18 patients (40.9%) were censored.

The median (95% CI) of OS in the ripretinib group was 65.6 (53.6, 65.6) weeks and that in the placebo group was 28.6 (17.9, 50.4) weeks. Compared with those in placebo group, the risk of death in patients receiving ripretinib decreased by 64% (HR 0.36; stratified log-rank test P = 0.0004).

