## 1.4 Study rationale

## **1.4.1** Rationale for the Study

There is no standard treatment for advanced or unresectable GIST patients after failure of imatinib, sunitinib and regorafenib. Secondary KIT mutations causing drug resistance are highly heterogeneous. Patients who failed prior treatments may have multiple acquired resistance-conferring mutations, and it is difficult to carry out clinical study in the population. There are very limited data that support the resuming of drugs which were ineffective in the past. A Korean, single-center, randomized, placebo-controlled study (RIGHT trial) showed that benefit from resuming imatinib (mPFS = 1.8 months) was less than that from using placebo (mPFS = 0.9 month). However, subgroup analysis in the study showed that accompanying symptoms of patients were not relieved, and health-related quality of life was assessed with EORTC QLQ-C30 questionnaire. RIGHT trial excluded patients who obtained limited benefit from initial imatinib treatment (defined as PFS  $\leq$  6 months). Therefore, patients who succeeded in initial imatinib treatment are inclined to be enrolled. Resuming imatinib is not the approved standard treatment worldwide. Many doctors choose imatinib as second-line treatment according to patients' medical history.

DCC-2618 is a pan KIT and PDGFRA inhibitor. In phase 1 study DCC-2618-01-001, all patients received adequate prior treatment and were resistant to TKI. DCC-2618 presented an encouraging anti-tumor effect (see Section 1.3.2 Clinical Summary for specific data). Phase 1 study results were consistent with non-clinical study results, indicating that DCC-2618 was effective on all tested KIT and PDGFRA mutations. For GIST patients who have received adequate prior treatments and are resistant to TKI, DCC-2618 can significantly decrease allete frequency with KIT exons 13, 14, 17 and 18 and PDGFRA D842V resistance-conferring mutations. The above observed clinical efficacy and decreased allele frequency support that DCC-2618 can effectively treat GIST patients who failed prior treatments (7 at most).

In view of the above basis, Deciphera carried out a phase 3, double-blind, placebo-controlled,

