## 5.3.2 Dose interruption and dose reduction due to adverse events

Treatment suspension and/or dosage reduction of the investigational drug or treatment termination will be allowed at any time during the study for subjects with an intolerant toxicity reaction of any levels. If the drug is resumed after dose suspension, calculation of visit cycle should be based on the predetermined arrangement and not influenced by dose suspension. See Table 6 for dose adjustment regimen.

If subjects can't tolerate 50 mg QD or experience disease progression based on independent radiology review after dose reduction, the study treatment should be terminated and subjects should enter the safety follow-up period and start survival follow-up.

All dose interruptions, reductions (including missed doses), downtitration, or uptitration, and reasons must be recorded on the eCRF form.

	Initial dose	First reduction	Second reduction
Initial Patient	150mg QD	100mgQD	50mg QD
Patients whose dosage are increased to 150 mg BID after disease progression	150mg BID	100mgBID	150mg QD

 Table 6 DCC-2618 Dose Modification Scheme

If the adverse event resolves to grade 1 or baseline level and the drug is resumed, the subject will be allowed to resume the drug at the dose when the adverse event occurred. If the dose

for the subject has been reduced to the first reduced dose and the adverse event resolves to grade 1 or baseline level, the subject will be allowed to resume the drug at the initial dose. If the subject has experienced two consecutive reductions and the adverse event resolves to grade 1 or baseline level, the subject will be only allowed to resume the drug at the first reduced dose for at least one cycle (28 days) continuously and then use the drug at the initial dose.

If the adverse event does not resolve to grade 1 or baseline level within 28 days, the study treatment should be discontinued, unless the investigator evaluates that the adverse event is not clinically significant. After discussing with the sponsor, there may be an opportunity to resume the drug at a dose reduced by one level.

dose adjustmen							
Severity of AE	Handling of AE and dose adjustment principles						
Grade 1	Provide symptomatic and supportive treatment, and continue the drug at the original dose.						
Grade 2	Provide symptomatic and supportive treatment, and continue the drug at the origin dose.						
	If the AE is not improved within 7 days, the treatment should be withheld:						

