## 9.4.5 Efficacy analysis

# 9.4.5.1 Primary endpoints:

# PFS analysis based on independent radiology review

PFS based on independent radiologic review is defined as the time from the first dose of investigational drug (C1D1) to the first documentation of disease progression based on independent radiologic review or death due to any cause (whichever occurs first). Subjects who have previously received surgery for target lesion or non-target lesion, those who have previously received other anti-tumor treatments, and those whose progression or death date is not recorded for any reasons will be censored on the day of the last assessment.

EAS will be used as the main analysis set, with PP as the supporting analysis set. Sensitivity analysis of progression-free survival will be performed, which will be further described in SAP.

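### The 1-month success threshold falls inside the ±7-day window of the first scan, so compliant late scans can produce a pass without drug effect

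*Combined protocol and SAP*

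**What the plan says.** Section 9.1 and the synopsis set one criterion for bridging success: "the lower limit of bilateral 90% confidence interval of the observed mPFS is longer than 1 month". The null median is 1 month and the alternative is 2.5 months. No conversion of a month to days is given.

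Section 9.4.5.1 measures PFS from Cycle 1 Day 1 (C1D1) "to the first documentation of disease progression based on independent radiologic review or death due to any cause". No rule moves an event to its scheduled visit date. The same section adds: "Sensitivity analysis of progression-free survival will be performed, which will be further described in SAP".

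A cycle is 28 days. The synopsis says that a "radiographic examination will be performed within $\pm 7$ days of each cycle", and note 17 to Table 1 asks for one scan per cycle through Cycle 4. Table 1 shows no on-treatment scan before Day 1 of Cycle 2 (C2D1).

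Two no-treatment medians are cited. Section 1.3.1.3.2 reports "that in the placebo group was 4.1 (4.0, 7.3) weeks", and Section 1.4.1 gives 0.9 month for placebo in an imatinib rechallenge trial.

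**The concern.** The decision point sits where a patient's recorded time depends on the appointment date. A patient who progresses during cycle 1 is recorded as an event before 1 month if scanned on time and after 1 month if scanned three days later (two if C1D1 is counted as day 1). Both scans comply. In a single-arm trial no control group shares the scan timing and cancels this.

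The cited placebo medians lie within about 3 days of the threshold: 4.1 × 7 = 28.7 days and 0.9 × 30.4 = 27.4 days. As reported, both would fail the rule. They do show that the rule must separate effect from no effect in the range that scan timing can shift. What is at stake is whether the rule can reject a weak result, not whether an effective drug would pass.

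**Working it through.** **The plan's own figure.** The proportion event-free at 1 month is 0.50 under the null and 0.5^(1/2.5) = 0.758 under the alternative. With one-sided 5% and 90% power,

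n = [(1.645 × √(0.5 × 0.5) + 1.282 × √(0.758 × 0.242)) / 0.258]² = 28.3, so 29; 29 / 0.85 = 34.1, so 35.

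The sample size reproduces and is not in dispute. It behaves like a test of the proportion event-free at 1 month, which is the quantity scan timing disturbs.

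**First-scan window.** 28 ± 7 gives 21 to 35 elapsed days, or 22 to 36 if C1D1 is day 1. This is inferred from Table 1 and the cycle length; no sentence states it as a day number. A month is taken as 30.4 days.

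**Pass rule in events.** The plan names Kaplan-Meier but no interval type, so the log-log form is assumed. With d events by the threshold and S = 1 − d/n, the lower limit is S^exp(1.645 × se), where se = √(d / (n(n − d))) / |ln S|. The trial passes if this exceeds 0.5.

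- n = 35: d = 12 gives 0.508 (pass); d = 13 gives 0.479 (fail).
- n = 30 (35 × 0.85 = 29.75): d = 10 gives 0.504 (pass); d = 11 gives 0.471 (fail).

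If exactly half of events are recorded by 1 month, P(Bin(35, 0.5) ≤ 12) = 4.5%. For documented mPFS the test therefore keeps its nominal level.

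**Adding scan timing.** Take underlying progression as exponential with median m. A first scan on day s records a cycle-1 progression before the threshold only if s ≤ 30.4, so

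p = mean over s of [1 − 2^(−s/m)] for s ≤ 30.4, and 0 otherwise.

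Example: m = 30.4, s uniform on 21 to 35. The share of scans by day 30.4 is 9.4/14 = 0.671. The mean of 1 − 2^(−s/30.4) over those days is about 0.443. So p ≈ 0.297 and P(Bin(35, p) ≤ 12) = 79%.

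Chance of passing, n = 35 (each range covers scans centred on day 28 or 29):

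| First scans | m = 28.7 days | m = 30.4 days |
|---|---|---|
| All on schedule | 4-6% | 7-9% |
| Uniform ±3 days | 17-48% | 22-55% |
| Uniform ±7 days | 73-84% | 79-88% |

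Other patterns, over both medians:

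- Normal spread: 6-15% with SD 1 day, 19-50% with SD 2 days.
- 10% of first scans after day 30.4, the rest on schedule: 13-21%. With 20% late: 29-41%.
- Shorter medians at ±7 days: 33-51% at 20 days, 7-18% at 14, 1-4% at 10.
- 20% of events as exactly dated deaths, ±7 days, m = 30.4: 60-71%.

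A Kaplan-Meier simulation with 15% dropout (4,000 runs, m = 30.4) gives 6-7% on schedule, 19-50% at ±3 days and 74-84% at ±7 days. A second simulation, with 30 evaluable patients and elapsed days, gives 70% (m = 28.7) and 76% (m = 30.4) at ±7 days. In that simulation, if every first scan is 3 days late, the trial passes 100% of the time, even at a 14-day median.

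**Length of the month.** With a 21-day median and every scan 2 days late, the second simulation passes about 100% of the time if a month is 28 days and about 0% if it is 30, 30.44 or 31. With scans 3 days late it passes at 28, 30 and 30.44 days, and about 0% at 31.

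**The case against.** The best case against has four parts.

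1. Progression cannot be documented before it occurs, so a reported placebo median of 27 to 29 days implies an underlying median no longer than that. At 20 to 24 days with modest spread the inflation is small: 0-1% on schedule, 0-2% with SD 1 day, 1-19% with SD 2 days, and 1-5% if 10% of scans are late. This stands, and it means that the highest figures describe an unfavourable case. However, the placebo upper limit of 7.3 weeks (51.1 days) leaves longer medians open, and 30.4 days is the plan's own null value.

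2. The ±7 days is a tolerance, not a distribution, and some events would carry actual dates through death or through the unscheduled scans allowed in Sections 6.6 and 6.10.1. If 30% did, the ±7-day result at a 20-day median would fall from 35-52% to 9-15%. This also stands: the size of the inflation depends on assumptions the documents cannot settle. Section 5.3.2 further limits drift, since "calculation of visit cycle should be based on the predetermined arrangement and not influenced by dose suspension", but the window remains.

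3. The test is stated for observed mPFS and is valid for it. That is true, but observed mPFS can exceed 1 month through timing alone, so a valid test of it need not show drug effect.

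4. Section 9 leaves details to an SAP to be finalised before database lock, which could define the month and the dating rule. What is promised there for PFS is sensitivity analysis, which would not change the success criterion. A rule settled that late could also be chosen with scan dates already known.

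**Conclusion.** The concern holds. Whichever usual length of month is used, the threshold lies inside the first-scan window, and scan timing that follows the plan exactly can decide success. At an underlying median of 28.7 to 30.4 days, the chance of a pass rises from 4-9% with on-schedule scans to 17-55% within ±3 days and 73-88% within ±7 days.

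That the flaw exists is certain; how large it is depends on the assumed scan spread, underlying median, exponential shape, share of exactly dated events and log-log interval. The sample size of 35 is unaffected, and a drug with the reference median of 27.6 weeks passes under any of these patterns. This should be fixed because it concerns the trial's only formal success criterion and the repair is cheap.

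**What to change.** In Section 9.1, define 1 month in days and state whether C1D1 is day 0 or day 1. Then take the decision point out of the scan window.

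- **Preferred.** For the success test only, date each independently reviewed progression found at a scheduled scan at its scheduled date (C2D1, C3D1 and so on). Leave deaths and progressions found at unscheduled scans at their actual dates, and keep the 1-month threshold. Say which scans count as scheduled and how a first scan outside the window is dated. This can only make the test stricter, because an early first scan moved to day 28 still counts as under a month of 30 or 31 days.
- **Alternative.** Require the lower limit to exceed day 36, the last day of the window with C1D1 as day 1. This moves the null to 36/30.4, about 1.2 months.

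Keep actual-date PFS as the descriptive estimate and report the distribution of first-scan days.

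The cost is wording in Sections 9.1 and 9.4.5.1 and the synopsis, with no extra patients or scans. All first-scan progressions then count. With centred scans, the chance of passing is 7-9% at a 30.4-day median and 4-6% at 28.7 days. Power at 2.5 months is 95-96% (n = 35) or 93-94% (n = 30). If all scans run 0 to 7 days late, power is 91-93% or 88-90%, so with 30 evaluable patients it can dip just below the planned 90%.

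Early scans still favour success, because less progression has occurred by then. At a 30.4-day median the chance of passing is 16-20% if scans spread over 0 to 7 days early, and 33-39% if all fall on the first day of the window. The present rule has the same exposure, and the plan should say so.
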